## **1.1      Objectives and endpoints**

No specific objectives are defined to specifically relate to the 56 weeks cut off. For the objectives related to PACO, please refer to the protocol.

All the details of the endpoints, assessments and timeframes for the week 56 cut-off are explained in the appendix 2.

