## 4 Analysis sets

For the purposes of analysis, the following analysis sets are defined for the week 56 cut-off.

Subject Analysis Set	Description
Full Analysis Set (FAS)	All subjects randomised to concizumab PPX or on-demand treatment or allocated to arms 3 or 4. Subjects from arms 1 and 2 will contribute to the evaluation ‘as randomised’.
Safety Analysis Set (SAS)	All subjects exposed to concizumab PPX or randomised to on-demand treatment. All subjects will contribute to the evaluation ‘as treated’.

Defined Analysis Data Sets	Description
On-treatment	
The time period where subjects are considered to be affected by on-demand treatment or concizumab treatment.
 
For safety endpoints/assessments relating to events (number of thromboembolic events, number of hypersensitivity type reactions, number of injection site reactions, number of patients with antibodies to concizumab, number of adverse events) the ‘on-treatment’ analysis data set is defined as follows.
 
For subjects in arm 1 during on-demand treatment, the period begins on the date of randomisation (as registered in IWRS) and ends at the first occurrence of:
 

1. Time of permanently ending on-demand administration and initiation of any PPX regimen

2. The last direct subject-site contact, at or prior to the 56 weeks cut-off

3. Withdrawal date for subjects who withdraw informed consent

4. The last subject-investigator/site contact as defined by investigator for subjects who are completely lost to follow up

5. Date of death for subjects

 
For subjects in arm 1 during concizumab PPX treatment, the period begins at the time of initiation of concizumab PPX treatment and ends at the first occurrence of:
 

6. Date of last dose of concizumab + 7 weeks

7. Items 2., 3., 4. or 5. above

 
For subjects in arms 2-4 that start on the new concizumab dosing regimen and who have not been exposed to the initial dosing regimen, the period begins at the time of start of the new concizumab PPX regimen.

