	
For subjects in arms 2-4 that are only exposed to the initial concizumab dosing regimen, the period begins at the time of start of the initial concizumab PPX regimen.
 
For subjects in arms 2-4 that start on the new concizumab dosing regimen and who have been exposed to the initial dosing regimen, the period consists of two periods with a pause in between. The first period begins at the time of start of the initial concizumab PPX regimen and ends 7 weeks after the treatment was paused while the second period begins at the time of start of the new concizumab PPX regimen.
 
For all cases of arms 2-4 above the periods end at the first occurrence of:
 

• Items 2., 3., 4., 5. or 6. above

On-treatment without data on initial regimen	
The time period where subjects are considered to be affected by on-demand treatment or treatment with the new concizumab dosing regimen.
 
The analysis data set is defined similarly as the ‘on-treatment’ analysis data set with the exception:
 

• Observation time during the initial concizumab PPX regimen is excluded

On-treatment without ancillary therapy a excl. data on initial regimen for subjects exposed to both regimens	
The time period where subjects are treated by either the new concizumab dosing regimen or the initial concizumab dosing regimen (only included if not exposed to the new concizumab dosing regimen) or are treated by on-demand treatment and additionally have not used factor-containing products not related to treatment of a bleed during any of the cases.
 
The analysis data set is defined similarly as the ‘on-treatment’ analysis data set with the exception:
 

• Periods where factor containing products not related to treatment of a bleed have been used are excluded

• For subjects in arms 2-4 that start on the new concizumab dosing regimen and who have been exposed to the initial dosing regimen, the data on the initial concizumab PPX regimen are excluded

a Ancillary therapy is defined as use of factor-containing products not related to treatment of a bleed.

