**Table 1 Analysis sets used for analyses and/or presentations of endpoints/assessments**

Endpoint/assessment categories a	Subject Analysis Set	Analysis Data Sets
Bleeding episodes	FAS	On-treatment without ancillary therapy excl. data on initial regimen for subjects exposed to both regimens
PK, PD and safety not relating to events	SAS	On-treatment without data on initial regimen
Safety relating to events b	SAS	On-treatment and On-treatment without data on initial regimen

aWhich endpoints/assessments that belong under each category can be found in section 9 of the protocol version 7.

bThis specifically refers to: number of thromboembolic events, number of hypersensitivity type reactions, number of injection site reactions, number of patients with antibodies to concizumab, and number of adverse events.

For arms 2-4 the target joints registered at baseline will be used for the assessment done at week 56. For arm 1 the target joint evaluation done at visit V9a will be used for assessment at week 56.

Continuous endpoints/assessments will be presented using descriptive statistics which will include min, max, mean, SD, median, and quartiles. For PK endpoints/assessments, the descriptive statistics will also include geometric mean and geometric CV. Event data (including AEs) will be summarised including number of subjects with an event/episode, percentage of subjects with an event/episode, number of events/episodes and rate of events/episodes. Categorical assessments will be summarised by number and percent of subjects in each category. Presentations of results will be by arm and visit (when applicable) and when relevant arm 1 will be split into two parts with on-demand treatment and concizumab treatment.

Baseline for the assessments done at week 56 is defined as the latest non-missing measurement recorded before the time of the first administration of concizumab with the new dosing regimen (arms 2-4 and arm 1 after receiving concizumab) or recorded before randomisation to the on-demand administration (arm 1). If this measurement is missing for arms 2-4 or a subject from arms 2-4 chooses not to restart on concizumab, then the baseline obtained prior to the initial dosing regimen will be used (if available). If the V9a measurement is missing for arm 1 concizumab part,

the latest measurement recorded prior to V9a will be used as a concizumab baseline for arm 1 subjects.

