Assessment	Endogenous thrombin potential (ETP)	At visits where thrombin generation assessments are planned to be measured in the trial up to 56 weeks	nmol/L*min		5.5.2
Assessment	Endogenous thrombin Potential ratio	At visits where thrombin generation assessments are planned to be measured in the trial up to 56 weeks	Ratio		5.5.2
Assessment	Velocity index	At visits where thrombin generation assessments are planned to be measured in the trial up to 56 weeks	nmol/L*min		5.5.2
Assessment	Thrombin lag time	At visits where thrombin generation assessments are planned to be measured in the trial up to 56 weeks	min		5.5.2

Assessment	Time to thrombin peak	At visits where thrombin generation assessments are planned to be measured in the trial up to 56 weeks	min		5.5.2
Assessment	Number of adverse events	On demand (arm 1) • From randomisation to on demand treatment up until start of concizumab treatment	Count	Week 56 cut-off is when all patients from arm 2-4 have completed visit 13a assessments or permanently discontinued treatment.	5.6.2
Assessment	Number of thromboembolic events	Concizumab (arm 1) • From start of the new concizumab dosing regimen up until week 56 cut-off	Count	Concizumab (arm 1) data available up until week 56 cut-off will be presented.	5.6.2
Assessment	Number of hypersensitivity type reactions	Concizumab (arms 2-4) • Before the pause: From start of concizumab treatment (week 0) up until 7 weeks after the treatment pause  as well as  • After the pause: From start of the new concizumab treatment (week 0) up until week 56 cut-off	Count		5.6.2
Assessment	Number of injection site reactions				5.6.2

Assessment	Number of patients with antibodies to concizumab	Concizumab (arms 2-4) 
 
From start of the new concizumab dosing regimen (week 0) up until week 56 cut-off
 
	Count	
Week 56 cut-off is when all patients from arm 2-4 have completed visit 13a assessments or permanently discontinued treatment.
	5.6.3

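### The SAP gives the week-56 antibody count two different scopes: Appendix 2 leaves out arm 1 and the pre-pause period, while Section 4 and Table 1 include arm 1 throughout and the pre-pause period in one of two data sets

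*SAP*

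**What the plan says.** SAP Section 1.1 makes Appendix 2 the place to look for time frames: "All the details of the endpoints, assessments and timeframes for the week 56 cut-off are explained in the appendix 2". The antibody row in Appendix 2 (Section 6.2) has its own time-frame cell, headed for arms 2–4 only: "From start of the new concizumab dosing regimen (week 0) up until week 56 cut-off". It has no arm 1 entry and no pre-pause entry. Its details cell also lacks the statement, present in the neighbouring event rows, that arm 1 concizumab data up to the cut-off will be shown.

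Table 1 in SAP Section 5.1 assigns safety assessments relating to events to the safety analysis set with two data sets, "On-treatment and On-treatment without data on initial regimen". Footnote b lists the members of that category by name, ending with "number of injection site reactions, number of patients with antibodies to concizumab, and number of adverse events". Section 4 names the antibody count in the same way when it defines the on-treatment data set.

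In Section 4 the on-treatment data set has these components:

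- For arm 1 during concizumab prophylaxis, "the period begins at the time of initiation of concizumab PPX treatment and ends at the first occurrence of" a list of stopping events.
- For arms 2–4 patients who received only the initial regimen, "the period begins at the time of start of the initial concizumab PPX regimen".
- For arms 2–4 patients who received both regimens, there are two periods, the first running to 7 weeks after the pause.

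The second data set is defined in the same way with one exception: "Observation time during the initial concizumab PPX regimen is excluded".

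**The concern.** The same count has one scope in the appendix that is meant to settle time frames and another in the sections that define and assign the data sets. A programmer working from Appendix 2 would leave out arm 1 on concizumab and everything before the pause. A programmer working from Section 4 and Table 1 would include arm 1 in both presentations and the pre-pause period in one. Both could claim to have followed the SAP.

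At stake is the numerator and denominator of a reported immunogenicity incidence. Under Appendix 2 the antibody count would also rest on a different population from the hypersensitivity count beside it, which includes arm 1 on concizumab and the pre-pause period. That makes the two harder to read together.

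**Working it through.** The SAP states no figure to reproduce, so the check sets the definitions side by side and then sizes the arm 1 part from planned enrolment.

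**Step 1. Who is in each scope** (SAP Appendix 2 antibody row against the two Section 4 data sets named in Table 1):

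| Group and period | Appendix 2 row | On-treatment | On-treatment, initial regimen removed |
|---|---|---|---|
| Arms 2–4, new regimen | in | in | in |
| Arm 1 on concizumab | out | in | in |
| Arms 2–4, both regimens, pre-pause period | out | in | out |
| Arms 2–4, initial regimen only | out | in | out |

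The Appendix 2 column differs from the last column in the arm 1 row and from the on-treatment column in three rows. It equals neither. If Appendix 2 were followed, the two presentations that Table 1 requires would also give the same antibody result, so one of them would lose its purpose.

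Section 4 formally includes arm 1 during on-demand treatment as well. That has little bearing here, because Protocol 9.4.7 gives arm 1 only the screening antibody sample in the main part.

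**Step 2. Which scope the other texts support.**

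- SAP Section 5.6.3, the section cited in the antibody row, says the count is presented as in Section 5.1, which leads back to Table 1.
- Protocol 4.3.2.2 defines the antibody endpoint at the primary analysis cut-off for arms 2–4 before and after the pause, plus the arm 1 extension.
- Protocol 9.4.7 requires antibody samples from all arms in the extension, so arm 1 data should exist.

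All three agree with the wider scope.

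**Step 3. The neighbouring rows.** Eleven rows of Appendix 2 point to SAP 5.6.2 or 5.6.3: adverse events, thromboembolic events, hypersensitivity, injection site reactions, antibodies, safety laboratory parameters, body weight, systolic and diastolic blood pressure, pulse and physical examination. Reading merged cells as one block, 10 of the 11 include arm 1 on concizumab; the antibody row is the exception. The event rows also carry the pre-pause window for arms 2–4: "Before the pause: From start of concizumab treatment (week 0) up until 7 weeks after the treatment pause".

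**Step 4. Size of the arm 1 omission** (Protocol Table 2):

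- Arm 1: 9 + 8 = 17
- Arm 2: 18 + 16 = 34
- Arm 3: up to 15 + 10 = 25
- Arm 4: 60
- Total: 17 + 34 + 25 + 60 = 136, which matches the enrolment stated in Protocol 5.1
- Appendix 2 row: at most 34 + 25 + 60 = 119
- Section 4 data sets: up to 119 + 17 = 136
- Arm 1 share: 17 / 136 = 12.5%

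The pre-pause omission cannot be sized. The documents give neither the number of patients exposed only to the initial regimen nor an expected antibody incidence.

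**The case against.** The best defence is that a time frame narrower than its data set need not be a contradiction. Section 5.1 applies Table 1 except where the SAP specifies something else, and Section 1.1 sends the reader to Appendix 2. Other rows are also narrower than their data sets. The bleeding rows start arms 2–4 at the new regimen although their data set keeps patients who received only the initial one, and the physical examination row has no on-demand window. The pre-dose concentration row has the same narrow window as the antibody row, so a deliberate restriction is possible.

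This does not settle the matter. Nothing in the SAP declares an exception for antibodies, Section 4 and footnote b include them by name, and Section 5.6.3 points back to Section 5.1. The bleeding and physical examination rows still keep arm 1 on concizumab. The concentration row's lack of a pre-pause window agrees with Table 1, which gives pharmacokinetics only the data set without the initial regimen; the antibody row has no such support.

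Several narrower points do stand:

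- Results are presented by arm, so post-restart counts for arms 2, 3 and 4 are the same under either reading. What is open is whether arm 1 appears, what any pooled total contains, and whether pre-pause positives are added.
- The mock tables and the analysis data reviewer's guide may resolve the scope in practice; they are not available here.
- The protocol plans the antibody count at the primary cut-off and again to the end of the trial, so the uncertainty concerns one intermediate summary.
- The count of 10 out of 11 depends on how merged cells are read and is supporting evidence only.

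**Conclusion.** The SAP is wrong as written on this point. The Appendix 2 antibody row fits neither data set to which Table 1 assigns the count. Followed literally, it would leave out up to 17 of 136 planned patients (12.5%), assuming all arm 1 patients start concizumab before the cut-off. It would also leave out the pre-pause presentation and, with it, patients exposed only to the initial regimen.

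The consequence is limited. The week-56 evaluation is descriptive, tests no hypothesis and supports no confirmatory conclusion. SAP 5.6.3 also plans a listing of all positive antibody results during the trial, so positives would not go unreported, although a listing gives no incidence. No claim is made about how many positives would be gained or lost.

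**What to change.** Rewrite the time frame of the antibody row with windows already used in the adjacent safety-event rows:

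- Arm 1: from start of the new concizumab regimen to the week-56 cut-off.
- Arms 2–4, before the pause: from start of concizumab to 7 weeks after the pause.
- Arms 2–4, after the pause: from start of the new regimen to the cut-off.

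Add the matching arm 1 statement to the details cell, and present the count on both Table 1 data sets. If the narrower scope is intended, give the reason in one sentence and amend the antibody entries in Section 4 and footnote b to agree with it.

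The cost is one table row, or one sentence and two matching edits. No new samples or data set definitions are needed. Because the SAP is final at version 2.0, the change requires a new version; version 2 was itself issued to correct one line of the on-treatment definition.

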***Novo Nordisk***

		be measured up until V13a (week 56)			
--	--	--	--	--	--
